## 1.6 Combination therapy utilizing ipilimumab and nivolumab

While the toxicity and clinical responses overlap, mechanisms of immune activation and range of responses appear to be different for ipilimumab and nivolumab. Preclinical data support the combinations of nivolumab and ipilimumab.[42]

The combination of nivolumab and ipilimumab (anti-cytotoxic T lymphocyte associated antigen-4 [anti-CTLA-4]) in a phase 1/2 trial showed markedly enhanced clinical activity with an acceptable safety profile in melanoma patients.[41] In the phase 1 study, nivolumab and ipilimumab were administered IV every 3 weeks for 4 doses followed by nivolumab alone every 3 weeks for 4 doses (concurrent regimen).[41] The combined treatment was subsequently administered every 12 weeks for up to 8 doses. In a sequenced regimen, patients previously treated with ipilimumab received nivolumab every 2 weeks for up to 48 doses. In the concurrent regimen (53 patients), 53% of patients had an OR at doses 1 mg/kg nivolumab and 3 mg/kg ipilimumab, with tumor reduction of 80% or more (modified World Health Organization [mWHO] criteria). In the sequenced-regimen (33 patients), the objective response rate (ORR) was 20%.

Tumor-cell expression (melanoma) of PD-L1 was characterized in combination with ipilimumab with the use of IHC staining and pharmacodynamics changes in the peripheral-blood absolute lymphocyte count.[41] With PD-L1 positivity defined as expression in at least 5% of tumor cells, biopsy specimens from 21 of 56 patients (38%) were PD-L1-positive. Among patients treated with the concurrent regimen of nivolumab and ipilimumab, ORs were observed in patients with either PD-L1-positive tumor samples (6 of 13 patients) or PD-L1-negative tumor samples (9 of 22). In the sequenced regimen cohorts, a higher number of overall responses was seen among patients with PD-L1-positive tumor samples (4 of 8 patients) than among patients with PD-L1-negative tumor samples (1 of 13) suggesting the possibility that these tumors have higher response rates to the combination. The relationship between PDL-1 expression and responses may not be present in patients treated with the combination. Tissue expression of PDL-2, interferon- $\gamma$  (IFN- $\gamma$ ), IDO, and T cell CD8+ are of current interest. Until more reliable data based on standardized procedures for tissue collection and assays are available, PD-L1 status cannot be used to select patients for treatment at this time.

For RCC results have been reported.[43] Pts were randomized to nivolumab 3mg/kg + ipilimumab 1mg/kg (n=21) and nivolumab 1mg/kg + ipilimumab 3mg/kg (n=23). Most pts (n=34; 77%) had prior systemic therapy (N3 + I1: 16; N1 + I3: 18). Objective response rate (ORR) was 29% (nivolumab 3mg/kg + ipilimumab 1mg/kg) and 39% (nivolumab 1mg/kg+ ipilimumab 3mg/kg.) Duration of response was 4.1 to 22.1 weeks (all 6 responses ongoing) in

nivolumab 3mg/kg + ipilimumab 1mg/kg, and 6.1 yo 18.3 weeks (8/9 responses ongoing) in nivolumab 1mg/kg+ ipilimumab 3mg/kg. Responses occurred by first tumor assessment at week 6 in 67% of responding patients in both patient cohorts. Stable disease was seen in 7 (33%) patients (nivolumab 3mg/kg + ipilimumab 1mg/kg) and 9 (39%) patients (nivolumab 1mg/kg + ipilimumab 3mg/kg). Treatment-related adverse events (AEs) were seen in 89% of patients with 16% discontinuation due to any-grade related AEs. Grade 3–4 related AEs 43%, most commonly ↑ lipase (16%, n=7), ↑ ALT (11%, n=5), diarrhea (9%, n=4), colitis (5%, n=2), ↑ amylase (5%, n=2). No grade 3–4 pneumonitis was seen. Based on the above background trials, the combination is being evaluated in other disease settings typically with 3mg/kg nivolumab and 1mg/kg ipilimumab q 3 weeks during induction, for 4 doses. This is the induction dosing we have chosen for the combination arm of the trial.

### **1.7 Rationale of 2 therapeutic arms of this trial**

There is interest in conducting 2 concurrent phase II studies exploring single agent nivolumab as well as the combination of nivolumab and ipilimumab. In metastatic melanoma, published data has demonstrated promising results with single agent nivolumab but the combination has been even more promising.

By conducting this study single agent efficacy of nivolumab will be determined. In addition, it will be explored if the combination arm leads to higher responses. This will be important to plan future clinical studies.

### **1.8 Rationale for crossover from single agent nivolumab to dual agent nivolumab/ipilimumab upon progression**

Recently published data has demonstrated superiority of responses with combination therapy with nivolumab and ipilimumab [49-52]. This data has shown near doubling of overall response rates across multiple diseases including, but not limited to melanoma, non-small cell lung cancer and renal cell carcinoma.

Given the high overall activity, the combination of nivolumab and ipilimumab was FDA approved for the treatment of metastatic melanoma. It was shown that the complete response rate with the combination was 17% versus none with nivolumab monotherapy for patients with melanoma. Further, ORR with the combination was found to be independent of PD-L1 status. In PD-L1–positive and –negative tumors, respectively, ORR was 58% and 55% with nivolumab/ipilimumab. More recently, frontline combination therapy with nivolumab and ipilimumab was demonstrated to be active in patients with non-small cell lung cancer receiving one of four dosing regimens of nivolumab and ipilimumab. It was noted that the ORR ranged from 13% to 39%, regardless of PD-L1 status. Further, in renal cell carcinoma, single agent nivolumab has demonstrated an ORR in 20% of patients while the combination of nivolumab and ipilimumab has demonstrated responses ranging from 43-48%.

Given the now known promise and overall higher degree of activity with the combination of nivolumab and ipilimumab, regardless of PD-L1 status in many other disease types- there is now rationale to allow a cross-over to dual therapy, for patients with locally advanced/metastatic sarcoma that have progressed on single agent nivolumab. Overall the 2-drug regimen appears to be more effective therapy than single agent, and while there is limited data in sarcoma, performing this crossover will provide access to dual agent therapy without affecting the integrity of the primary endpoint of the study and scientific design. Many of these patients will be excluded from future clinical trials with checkpoint blockade, as most trials will exclude patients with prior exposure to nivolumab. Also, sarcoma currently has minimal FDA approved

therapies and clinical trials are a mainstay of treatment. Therefore, with Update #04 of the protocol, the option of allowing re-registration and crossover to dual agent therapy, upon progression on single agent nivolumab, was added to the protocol.

## 1.9 Rationale for cohort expansion in GIST

GIST are the most common sarcomas of the digestive tract and are thought to arise from or share a common ancestor with the interstitial cells of Cajal, the autonomic pacemaker cells of the gut that coordinate peristalsis. Approximately 4000 to 6000 new cases of GIST are diagnosed in the US each year. Between 75% and 80% of these tumors contain activating mutations of KIT or PDGFR-alpha, providing oncogenic signaling and driving tumor growth. Given this, multiple small molecule tyrosine kinase inhibitors (TKI) against KIT and PDGFRA, such as imatinib, sunitinib, sorafenib and dasatinib, have been evaluated for the treatment of this disease.

Advanced GIST is refractory to conventional chemotherapy or radiotherapy, but multiple TKIs have been shown to have antitumor activity in this disease. Imatinib mesylate, a multi-targeted TKI with activity against PDGFR, KIT, BCR-ABL, ABL and LCK, has become the first line standard of care in advanced GIST achieving disease control in 70% to 85% of patients, with a median progression free survival of 20 to 24 months. Although treatment with imatinib has greatly increased survival and quality of life for patients with advanced GIST, a subset of patients acquire kinase mutations in KIT or PDGFR-alpha that interfere with imatinib activity and ultimately lead to imatinib resistance.

At time of progression, the currently accepted treatment strategies include dose escalation of imatinib or transition to treatment with sunitinib. Sunitinib is a multi-targeted TKI with a kinase spectrum including VEGF as well as PDGFR and KIT, among others. In an international phase III trial of imatinib refractory patients, sunitinib showed a median time to tumor progression of 27.3 weeks compared to 6.4 weeks in those on placebo. Based on this and other data, sunitinib has been FDA approved for the treatment of imatinib-refractory or intolerant advanced GIST.

Although treatment of GIST with tyrosine kinase inhibitors results in demonstrated clinical benefit, this efficacy is not indefinite and treatment with KIT inhibition does not result in the cure of patients with advanced disease. Alternate options are necessary to improve outcomes for patients with TKI resistant GIST.

An attractive potential therapy for GIST is immunotherapy. There is pre-clinical evidence of benefit from immunotherapy in GIST. A study of 50 sarcoma patients treated at Memorial Sloan-Kettering Cancer Center consented to a tissue procurement protocol and collected correlative clinical information. Immunohistochemistry staining of tumor specimens was performed with the use of a rabbit monoclonal antihuman PD-L1 antibody (clone 28-8) and an automated assay developed by Dako. Findings were the following: there was >1% PDL-1 expression in 6/50 (12%) of samples that included all sarcoma subtypes. Positive PD-L1 expression was noted in 27% of GIST samples. Of all tested histologies, the highest level of expression was noted in GIST.

The high PD-L1 expression noted in GIST tumor samples prompted further pre-clinical work in this disease. In collaboration with the [name] lab, PD-L1 expression in tumor samples was re-explored as well as the efficacy of PD-1 blockade and sunitinib in mouse models. Over half of resistant GIST specimens contain intratumoral CD8 T cells that express substantial levels of PD-L1.

GIST is a malignancy with a marked difference in pathogenesis and treatment, compared to other sarcomas. The standard cytotoxic agents that are utilized in sarcoma are ineffective in GIST, and tyrosine kinase inhibitors are the standard of care. As described above, pre-clinical data suggests that PD-L1 expression is much higher in GIST compared to other sarcomas,

therefore, there is rationale to evaluate these agents in GIST, as separate cohorts given the overall different biology.

### **1.10 Rationale for cohort expansion in UPS/MFH and LPS**

Recent data from ASCO 2016 by Hussein Tawbi et al. noted efficacy of pembrolizumab in selected sarcomas. In a trial that enrolled 80 sarcoma patients, 40 bone (Ewing's, Osteosarcoma, Chondrosarcoma) and 40 soft tissue (leiomyosarcoma [LMS], undifferentiated pleomorphic sarcoma [UPS]/malignant fibrous histiocytoma [MFH], dedifferentiated/pleomorphic liposarcoma [LPS], synovial sarcoma), the overall response rate was 19.5%. There were higher responses in the MFH/UPS and LPS subtypes, tumors thought to be characterized by high mutational burden and high tumor infiltrating lymphocytes. Given the promising activity in these subtypes there is rationale to expand the trial in these 2 histologies.

### **1.11 Registration Quality of Life (QOL) Measurements**

QOL measurements of fatigue and overall perception of QOL are routinely included in Alliance studies and will be assessed upon registration in this study. Evidence has arisen indicating that baseline single-item assessments of fatigue and overall QOL are strong prognostic indicators for survival in cancer patients, independent of performance status. This evidence was derived from two separate meta-analyses recently presented at ASCO, the first involving 23 NCCTG and Mayo Clinic Cancer Center oncology clinical trials, the second involving 43 clinical trials. Routine inclusion of these measures should be considered similar to that of including performance status, either as stratification or prognostic covariates. It will take approximately one minute to complete this measure. [44]

### **1.12 Impact of This Trial**

Sarcomas represent a heterogeneous group of neoplasms with a limited number of therapeutic options in metastatic disease. There is indirect evidence from preclinical analysis of markers such as PDL-1 and characterization of immune infiltrates in human tissue samples that certain sarcomas may benefit from immune checkpoint blockade. This trial will represent one of the first Phase II studies of immune checkpoint blockade in sarcomas, and the first to combine CTLA-4 and PD-1 blockade in sarcoma. Planned correlates will investigate retrospective biomarkers that may predict which patients will respond to these therapies.

## **2.0 OBJECTIVES**

As of Update #06, the study objectives will be evaluated within the initial cohort of patients enrolled, as well as within 3 cohorts of patients defined by the following histologic subtypes: LPS, UPS/MFH, and GIST.

### **2.1 Primary objective**

To evaluate the confirmed response rate of single agent nivolumab and dual agent nivolumab plus ipilimumab in patients with locally advanced/unresectable or metastatic soft tissue sarcoma.

### **2.2 Secondary objectives**

**2.2.1** To evaluate adverse event rates (NCI CTCAE v4.0) within each treatment arm.

**2.2.2** To evaluate duration of response, clinical benefit rate, time to progression, progression-free survival, and overall survival within each treatment arm.

### **2.3 Correlative science objectives**

**2.3.1** To potentially detect an early signal of confirmed response rate within a histologically defined patient cohort.

**2.3.2** To assess the potential association between PD-L1 expression (by IHC) and clinical outcome, within each treatment.

**2.3.3** To evaluate associations between selected biomarker measured in serial peripheral blood and with clinical efficacy, within each treatment.

**2.3.4** To evaluate the association between selected biomarker measured in tumor tissue with clinical efficacy, within each treatment.

**2.3.5** To evaluate the association between baseline tumor mutational burden and neoantigen production with clinical efficacy within each treatment.

### **2.4 Exploratory Phase II objectives (Crossover Treatment)**

**2.4.1** To evaluate secondary endpoints within patients crossing over to dual agent nivolumab plus ipilimumab after experiencing progressive disease while receiving single agent nivolumab.

**2.4.2** To evaluate correlative science objectives endpoints within patients crossing over to dual agent nivolumab plus ipilimumab after experiencing progressive disease while receiving single agent nivolumab.

### 3.0 PATIENT SELECTION

For questions regarding eligibility criteria, see the [Study Resources](#) page. Please note that the Study Chair cannot grant waivers to eligibility requirements.

#### 3.1 On-Study Guidelines

This clinical trial can fulfill its objectives only if patients appropriate for this trial are enrolled. All relevant medical and other considerations should be taken into account when deciding whether this protocol is appropriate for a particular patient. Physicians should consider the risks and benefits of any therapy, and therefore only enroll patients for whom this treatment is appropriate.

Although they will not be considered formal eligibility (exclusion) criteria, physicians should recognize that the following may seriously increase the risk to the patient entering this protocol, and the following patients will not be enrolled:

- Medical condition such as uncontrolled infection, uncontrolled diabetes mellitus or cardiac disease which, in the opinion of the treating physician, would make this protocol unreasonably hazardous for the patient.
- Patients with a “currently active” second malignancy other than non-melanoma skin cancers. Patients are not considered to have a “currently active” malignancy if they have completed therapy and are free of disease for  $\geq 1$  year.

In addition:

- Women and men of reproductive potential should agree to use an appropriate method of birth control throughout their participation in this study and continue for 5 months (women) and 7 months (men) after the last dose of study drugs, even if oral contraceptives are also used, due to the teratogenic potential of the therapy utilized in this trial. Appropriate methods of birth control include abstinence, oral contraceptives, implantable hormonal contraceptives or double barrier method (diaphragm plus condom).
- Patients with a history of CHF or at risk because of underlying cardiovascular disease or exposure to cardiotoxic drugs as clinically indicated should be assessed as per the study calendar (see Section 5.0) for appropriateness for participation on this trial.

## 3.2 Pre-Registration Eligibility Criteria

Use the spaces provided to confirm a patient's eligibility by indicating Yes or No as appropriate. It is not required to complete or submit the following pages.

When calculating days of tests and measurements, the day a test or measurement is done is considered Day 0. Therefore, if a test were done on a Monday, the Monday four weeks later would be considered Day 28.

A female of childbearing potential is a sexually mature female who: 1) has not undergone a hysterectomy or bilateral oophorectomy; or 2) has not been naturally postmenopausal for at least 12 consecutive months (i.e., has had menses at any time in the preceding 12 consecutive months).

### 3.2.1 Central pathology review submission

Patients must have a FFPE tumor block OR 1 representative H&E and 20 unstained sarcoma tissue slides available for submission for central pathology review. This review is mandatory prior to registration to confirm eligibility. See [Section 6.2](#) for details on slide/block submission.

## 3.3 Registration Eligibility Criteria

### 3.3.1 Documentation of Disease

Histologic Documentation:

**Prior to Update #06:** Patients must have histologically confirmed bone or soft tissue sarcoma by central pathology review.

**Effective with Update #06:** Patients must have histologically confirmed LPS (only dedifferentiated and pleomorphic. Well differentiated not eligible), UPS/MFH, or GIST.

### 3.3.2 Disease Status

Measurable disease as defined in [Section 11.0](#).

Locally advanced/unresectable or metastatic disease.

### 3.3.3 Prior Treatment

- $\geq 1$  prior systemic therapy for sarcoma, including adjuvant systemic therapy.
- No prior therapy with ipilimumab or nivolumab, or any agent targeting PD-1, PD-L1 or CTLA-4.
- No treatment with biologic therapy, immunotherapy, chemotherapy, investigational agent for malignancy, or radiation  $\leq 28$  days before study registration. No treatment with nitrosourea or mitomycin  $\leq 42$  days before study registration. For GIST, tyrosine kinase inhibitor can be continued for up to 3 days prior to initiation of study treatment.
- Patients should have resolution of any toxic effects of prior therapy (except alopecia) to NCI CTCAE, Version 4.0, grade 1 or less.

### 3.3.4 No history of the following:

- Active known or suspected autoimmune disease. [See Appendix IV](#) for details.
- Patients with HIV are eligible if the lymphocytes  $> 350$  CD4+ cells and no detectable viral load
- Symptomatic, untreated, or uncontrolled brain metastases present.

- Active autoimmune colitis
- Autoimmune panhypopituitarism
- Autoimmune adrenal insufficiency
- Known active hepatitis B or C

**Hepatitis B Can be defined as:**

1. HBsAg > 6 months
2. Serum HBV DNA 20,000 IU/ml (105copies/ml), lower values 2,000-20,000 IU/ml (104-105 copies/ml) are often seen in HBeAg-negative chronic hepatitis B
3. Persistent or intermittent elevation in ALT/AST levels
4. Liver biopsy showing chronic hepatitis with moderate or severe necroinflammation

**Hepatitis C can be defined as:**

1. Hepatitis C AB positive
  2. Presence of HCV RNA
- Known active pulmonary disease with hypoxia defined as
    1. Oxygen saturation < 85% on room air or
    2. Oxygen saturation <88% despite supplemental oxygen

\_\_\_ **3.3.5 Concomitant Medications:**

No systemic treatment with either corticosteroids (> 10 mg daily prednisone equivalents) or other immunosuppressive medications within 14 days of registration.

\_\_\_ **3.3.6 Not pregnant and not nursing,** because this study involves an agent that has known genotoxic, mutagenic and teratogenic effects.

Therefore, for women of childbearing potential only, a negative pregnancy test done  $\leq 7$  days prior to registration is required.

\_\_\_ **3.3.7 Age  $\geq 18$  years**

\_\_\_ **3.3.8 ECOG Performance Status 0 or 1.**

\_\_\_ **3.3.9 Required Initial Laboratory Values:**

Absolute Neutrophil Count (ANC)	$\geq 1,500/\text{mm}^3$
Platelet Count	$\geq 100,000/\text{mm}^3$
Creatinine	$\leq 1.5 \times$ upper limit of normal (ULN) OR
Calc. Creatinine Clearance	$> 45 \text{ mL/min}^*$
Total Bilirubin	$\leq 1.5 \times$ upper limit of normal (ULN)**
AST / ALT	$\leq 3 \times$ upper limit of normal (ULN)
TSH	WNL***

\* Using the lean body mass formula only (Modified Cockcroft and Gault; Shargel and Yu 1985)

\*\* In absence of Gilbert disease (Total Bilirubin  $\leq 3 \times$  ULN with Gilbert). Also, if hyperbilirubinemia is clearly attributed to liver metastases total bilirubin  $\leq 3 \times$  ULN is permitted

\*\*\* Supplementation is acceptable to achieve a TSH WNL. In patients with abnormal TSH if Free T4 is normal and patient is clinically euthyroid, patient is eligible.

### 3.4 Re-registration Eligibility Criteria (For patients who crossover from arm 1 nivolumab alone to dual agent nivolumab and ipilimumab upon progression)

#### 3.4.1 Disease Status

- Measurable disease as defined in [Section 11.0](#).
- Locally advanced/unresectable or metastatic disease.
- Patient MUST have had progressive disease (radiographic or clinical) while on arm 1 single agent nivolumab while registered to A091401.

#### 3.4.2 Prior Treatment

- Patients removed from any immunotherapy for reasons other than progressive disease, including arm 1 single agent nivolumab of A091401, are NOT eligible for re-registration
- Patients must have completed a minimum of 10 weeks of single agent nivolumab on arm 1 of A091401 to be eligible for re-registration
- Patients must have completed study drug on arm 1 of A091401 (i.e., last dose of nivolumab)  $\leq$  12 months of re-registration to crossover dual agent therapy
- No treatment with immunotherapy  $\leq$  21 days before re-registration. No treatment with biologic therapy, chemotherapy, investigational agent for malignancy, or radiation  $\leq$  28 days before re-registration. No treatment with nitrosourea or mitomycin  $\leq$  42 days before re-registration.
- Patients should have resolution of any toxic effects of prior therapy (except fatigue and alopecia) to NCI CTCAE, Version 4.0, grade 1 or less, including immune toxicity.

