**The following tables provide protocol specific instructions for continuing administration of the investigational agent.**

*Generally we strongly encourage early evaluation, withholding drug, and appropriate treatment as indicated in the management tables and following event specific guidelines.*

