### 8.2.2 Dose Modification

Skin Rash and Oral Lesions	Management/Next Dose for Nivolumab and Ipilimumab
Grade 1	Continue on protocol therapy*
Grade 2	Continue on protocol therapy.*
Grade 3	Hold** until ≤ Grade 1. Resume nivolumab/ipilimumab at same level*
Grade 4	Off protocol therapy
*Steroid use does not require discontinuation of protocol therapy.	
**Any grade Steven Johnson syndrome requires discontinuation of protocol therapy.	
Recommended management: See Skin AE management algorithm	

Liver Function ALT AST Bilirubin	Management/Next Dose for Nivolumab and Ipilimumab
Grade 1	Continue protocol therapy*
Grade 2	Hold therapy until ≤ grade 1 then restart nivolumab/ipilimumab at same dose.*
Grade 3	Off protocol therapy
Grade 4	Off protocol therapy
*Steroid use does require discontinuation of protocol therapy.	
Recommended management: see Hepatitis AE management algorithm	

Colitis**	Management/Next Dose for Nivolumab and Ipilimumab
Grade 1	Continue protocol therapy*
Grade 2	Hold therapy until $\leq$ Grade 1*, then restart nivolumab at same dose. Discontinue ipilimumab.
Grade 3	Off protocol therapy.
Grade 4	Off protocol therapy.
See GI AE Algorithm for management of symptomatic colitis. *Steroid use does not require discontinuation of protocol therapy. **Follow this table for diarrhea when the workup shows objective evidence of autoimmune colitis.	
Recommended management: see GI AE management Algorithm	

Diarrhea**	Management/Next Dose for Nivolumab and Ipilimumab
Grade 1	Continue protocol therapy
Grade 2	Hold until $\leq$ Grade 1*, then restart nivolumab/ipilimumab at same dose.
Grade 3	Hold until $\leq$ Grade 1*, then restart nivolumab/ipilimumab at same dose.
Grade 4	Hold until $\leq$ Grade 1*, then restart nivolumab/ipilimumab at same dose.
*Steroid use does not require discontinuation of protocol therapy. **Follow this table for diarrhea when the workup shows no objective evidence of autoimmune colitis	

Pancreatitis**	Management/Next Dose for Nivolumab and Ipilimumab
Grade 2	Continue on protocol therapy*
Grade 3	Hold therapy until $\leq$ grade 2 then restart nivolumab/ipilimumab at same dose.*
Grade 4	Off protocol therapy
*Steroid use does require discontinuation of protocol therapy. **Patients who have asymptomatic amylase or lipase elevation may have a self-limited course and may continue therapy.	

Pneumonitis	Management/Next Dose for Nivolumab and Ipilimumab

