Grade 1	Hold dose pending evaluation. Resume nivolumab/ipilimumab if lymphocytic pneumonitis is excluded.*
Grade 2	Hold until $\leq$ Grade 1*, then restart nivolumab/ipilimumab at same dose.
Grade 3	Off protocol therapy.
Grade 4	Off protocol therapy
*Steroid use does require discontinuation of protocol therapy.	
Recommended management: See Pulmonary Adverse Event Management Algorithm	

Gastritis, nausea, vomiting	Management/Next Dose for Nivolumab and Ipilimumab
Grade 1	Continue protocol therapy*
Grade 2	Hold pending evaluation for gastritis duodenitis and other immune adverse events or other causes. Resume nivolumab/ipilimumab at same dose level after resolution to Grade $\leq$ 1.*
Grade 3	Hold pending evaluation until $\leq$ Grade 1. Resume nivolumab at same dose level.* If symptoms do not resolve within 7 days with symptomatic treatment, patients should go off nivolumab. Discontinue ipilimumab.
Grade 4	Off protocol therapy
*Steroid use does not require discontinuation of protocol therapy.	

Fatigue	Management/Next Dose for Nivolumab and Ipilimumab
Grade 1	Continue protocol therapy.
Grade 2	Continue protocol therapy.
Grade 3	Hold until $\leq$ Grade 2. Resume nivolumab/ipilimumab at same dose level.*
*Steroid use does not require discontinuation of protocol therapy.	

Neurologic events **	Management/Next Dose for Nivolumab and Ipilimumab
Grade 1	Hold dose pending evaluation. Once evaluation is complete, resume nivolumab/ipilimumab at same dose level.*
Grade 2	Hold dose pending evaluation and observation. Hold until $\leq$ Grade 1 and then resume nivolumab/ipilimumab at same dose level.*
Grade 3	Off protocol therapy
Grade 4	Off protocol therapy
*Steroid use does require discontinuation of protocol therapy. **Patients with any grade CNS events of aseptic meningitis, encephalitis, symptomatic hypophysitis, or myopathy, polymyositis, rhabdomyolysis, peripheral demyelinating neuropathy, cranial neuropathy (other than peripheral n. VII), GB syndrome, myasthenia gravis should be off study once diagnosed.	
Recommended management: See Neurologic Adverse Event Management Algorithm	

Endocrine Toxicity**	Management/Next Dose for Nivolumab and Ipilimumab
Grade 1	Continue protocol therapy.*
Grade 2	Hold until $\leq$ Grade 1 and patients are on a stable replacement hormone regimen, then resume nivolumab/ipilimumab at same dose level.*
Grade 3	Off protocol therapy.***

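### The crossover criteria in 3.4.2 do not expressly bar Arm 1 patients with past, resolved Grade 2 or higher autoimmune colitis from starting ipilimumab

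*Combined protocol and SAP*

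**What the plan says.** Sections 7.2 and 12.2 allow an Arm 1 patient who progresses to re-register and start both drugs, with eligibility judged under section 3.4.

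Two bullets of 3.4.2 bear on past toxicity. The first makes ineligible "Patients removed from any immunotherapy for reasons other than progressive disease". The last asks for "resolution of any toxic effects of prior therapy (except fatigue and alopecia) to NCI CTCAE, Version 4.0, grade 1 or less, including immune toxicity". The time limit is that the last nivolumab dose falls within "12 months of re-registration to crossover dual agent therapy". Section 3.4.3 adds a 14-day bar on steroids above 10 mg a day of prednisone equivalent and on other immunosuppressants.

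During treatment, the colitis table in 8.2.2 says that Grade 2 is held until Grade 1 or less, and "then restart nivolumab at same dose. Discontinue ipilimumab". Grade 3 and Grade 4 end protocol therapy. Its footnote gives the scope: "Follow this table for diarrhea when the workup shows objective evidence of autoimmune colitis". Section 8.2 introduces all these tables as "protocol specific instructions for continuing administration of the investigational agent".

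At first registration, the list in 3.3.4 headed as conditions with no history includes "Active autoimmune colitis". Section 3.4 does not repeat that item.

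**The concern.** For a patient already on both drugs, the protocol treats Grade 2 autoimmune colitis as a reason to give no more ipilimumab, even though nivolumab may go on. A crossover patient with the same event in the recent past can meet every item in 3.4 and then be offered four doses of ipilimumab.

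What is at stake is patient safety. Section 8.1.10 warns of perforation with colitis. The ipilimumab risk list in 9.4.2 includes colonic perforation and warns of severe and fatal immune-mediated events. The nursing guidance in 10.2 says that immune-mediated effects tend to be more frequent on the combination. With no explicit rule in 3.4, sites may decide the same case differently.

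**Working it through.** No arithmetic applies. The check traces a patient through the text and asks at each step whether anything stops crossover.

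**Which criteria govern.** Sections 7.2 and 12.2 point to 3.4, and 12.2 adds re-registration under 4.6. At that step the registration office confirms progression and that data are up to date; no check of toxicity history is stated.

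**Route A: colitis on nivolumab.** Grade 2 autoimmune colitis leads to a hold, recovery and a restart of nivolumab, and the colitis table says steroid use does not force discontinuation. The patient has not been removed. Under 8.2 the patient stays on drug if the hold is no longer than 6 weeks, there are no more than two delays for the same event, and nothing beyond steroids is needed. If progression follows after at least 10 weeks of nivolumab, the reason for removal is progression, so the first bullet of 3.4.2 is passed. If the colitis is at Grade 1 or less and steroids are low, the last bullet and 3.4.3 are passed too.

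**Route B: colitis after removal for progression.** The reason for removal is fixed as progression before the colitis starts, so the first bullet cannot catch it. Re-registration is possible from more than 21 days after the last immunotherapy until 12 months after the last nivolumab dose. The nursing guidance in 10.2 says side effects can appear months after stopping. Once the event has settled, the last bullet is passed. The limits in 8.2 act on patients receiving study drug, so they do not apply on this route.

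| Autoimmune colitis | Rule during treatment (8.2.2) | Result at crossover (3.4) |
|---|---|---|
| Grade 2 on nivolumab, resolved, drug resumed, later progression | ipilimumab stopped, nivolumab restarted | not barred |
| Grade 2 after removal for progression, resolved | ipilimumab stopped, nivolumab restarted | not barred |
| Grade 3 or 4 after removal for progression, resolved | all protocol therapy ended | not barred |
| Grade 3 or 4 on nivolumab | all protocol therapy ended | barred: removed for a reason other than progression |
| Still above Grade 1 at re-registration | held or off, by grade | barred: current grade |

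The first three rows are the gap. The last two show what 3.4 already covers.

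**Other text that might close it.**
- 3.1 leaves unsuitable conditions to the treating physician and says its list is not formal exclusion criteria.
- 3.3.4 and Appendix IV, which covers a history of autoimmune disease that might recur, are invoked at first registration only.
- The crossover part of 13.7 suspends re-registration for the group once events have accumulated. It is not a bar on an individual patient.

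**The case against.** The strongest reply is that 8.2.2 already answers the question. The Grade 2 colitis row covers the next dose of both drugs and has no arm limit. Section 8.2.1 refers to 7.2 as well as 7.0. Crossover is also treated partly as continuation: 7.2 counts earlier nivolumab toward the 108 weeks, and 12.2 resumes cycle numbering from the last cycle received. A cautious site could fairly read the row as barring ipilimumab. This stands as a possible reading, and it is why the point is an unclosed gap and not two rules in conflict. It does not settle the matter. The tables are framed as covering continued dosing, the row is worded for a drug already being given, and 3.4, 7.2 and 12.2 do not refer to it.

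A second reply is that the difference may be deliberate. In Arm 2 the colitis arose on ipilimumab; in Arm 1 it arose on nivolumab, which the protocol allows to restart. The mention of immune toxicity in 3.4.2 shows that resolved events were considered. This also stands in part: the documents give no rate showing that resolved nivolumab colitis raises the risk on ipilimumab. But they give no reason for admitting these patients either, and the on-treatment rule points the other way. On route B, the text admits a patient with past Grade 3 or 4 colitis who would have been barred had the same event occurred on nivolumab.

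Third, a crossover patient is not unprotected. Recurrent Grade 2 colitis would stop ipilimumab, and Grade 3 or 4 would end protocol therapy. That is true, but it acts only after re-exposure.

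A reader might infer that 3.4 has no safeguard against colitis at all. It does: the grade criterion and the steroid limit cover current disease. The colitis item in 3.3.4 contrasts with 3.4 only if it is read as history, and the word active favours current disease.

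**Conclusion.** The point holds for past, resolved autoimmune colitis only. Section 3.4.2 does not expressly bar a patient on route A (Grade 2 on nivolumab) or route B (Grade 2 or higher after removal for progression), although 8.2.2 would stop ipilimumab or all protocol therapy for the same events on treatment.

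The size is small and cannot be estimated. The documents give neither a Grade 2 colitis rate on nivolumab alone nor the crossover uptake, and each case needs colitis, recovery, progression and re-registration together. A reader might try to derive a count from the nivolumab risk list in 9.4.1, which places colitis in its 20%-or-less column. That is a column limit for any grade, before all those conditions, and says little. Nor does the renal cell study in 1.6 give the risk after crossover: its 2 colitis cases in 44 patients pool 23 given ipilimumab at 3 mg/kg, three times the dose here, and nothing is said about prior colitis.

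This is a minor safety alignment. It rests on reading 3.4 as the complete crossover criteria, as 7.2 and 12.2 direct, and on the on-treatment colitis rule being the protocol's own view of ipilimumab after such an event.

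**What to change.** Add a bullet to 3.4.2: *Patients who had Grade 2 or higher colitis, with objective evidence of autoimmune colitis and at least possibly related to study drug, during or after Arm 1 nivolumab are not eligible for re-registration, even if it resolved and nivolumab was resumed.* Add a cross-reference to this bullet in the colitis table of 8.2.2. If the sponsor does intend to admit such patients, 3.4.2 should say so and give the reason.

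The change is one sentence and one cross-reference at the next update, checked against the patient's record at re-registration. The primary endpoint is untouched, because 13.3 excludes data after crossover, and the crossover analyses are exploratory. The real cost is that a few recovered patients lose dual therapy, in a disease where section 1.8 says that few therapies are approved and that many of these patients will be shut out of other checkpoint trials. Limiting the bar to objectively shown, drug-related colitis of Grade 2 or higher keeps that loss small.
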